5.1.3 Dose Modifications for Other Sorafenib-Associated Toxicity

Toxicity	Grade 1	Grade 2	Grade 3*	Grade 4*
Non-hematologic	Continue at the same dose level.	Continue at the same dose level.	Withhold dose until toxicity is grade ≤ 1 , then resume treatment at the same dose level. If patient experiences a second grade 3 toxicity, withhold dose until toxicity is grade ≤ 1 , then reduce one dose level and resume treatment.	Withhold dose until toxicity is grade ≤ 1 , then reduce one dose level and resume treatment, or discontinue at the discretion of the principal investigator.
Hematologic	Continue at the same dose level.	Continue at the same dose level.	Withhold dose until toxicity is grade ≤ 2 , then resume treatment at the same dose level. If patient experiences a second grade 3 toxicity, withhold dose until toxicity is grade ≤ 2 , then reduce one dose level and resume treatment.	Withhold dose until toxicity is grade ≤ 2 , then reduce one dose level and resume treatment, or discontinue at the discretion of the principal investigator after discussion with study supporter.

*Patients who develop grade 3 fever/chills, grade 3 hyperlipasemia or hyperamylasemia without clinical or other evidence of pancreatitis, grade 3 leukopenia, or grade 3/grade 4 lymphopenia may continue study treatment without interruption at the discretion of the investigator.

Because certain grade 3-4 adverse events are common with epirubicin, ifosfamide and radiotherapy, the above table should be modified for these adverse events as defined below (unless the adverse events are definitely attributable only to sorafenib, in which case refer to above table). Attribution to sorafenib at least in-part should be present in order to justify sorafenib dose-reduction:

- Neutropenia – Grade 3 or Grade 4 lasting ≤ 7 days: no action. Grade 4 lasting > 7 days: refer to table above
- Neutropenic Fever – Grade 3 lasting ≤ 5 days: no action. Grade 3 lasting > 5 days or Grade 4: refer to table above
- Leukopenia – No dose reduction
- Thrombocytopenia -- Grade 3: no action. Grade 4 lasting ≤ 5 days: no action, Grade 4 lasting > 5 days: refer to table above. Grade 3-4 thrombocytopenia with clinically significant bleeding: refer to table above.
- Anemia – Grade 3: no action. Grade 4: refer to table above

- Nausea/Vomiting – Per above table, only if persistent Grade 3-4 despite maximal anti-emetic adjustment
- Fatigue – Grade 3: no action. Grade 4: refer to table above.
- Diarrhea – Diarrhea should be initially managed with anti-diarrhea agents including loperamide or Lomotil. If persistent Grade 3- 4 toxicity, refer to table above.
- Hypophosphatemia/Hypokalemia – Grade 3: replacement therapy. Grade 4: refer to above table only if refractory to replacement therapy
- Transaminitis – Grade 3 with ALT and AST: Monitor liver function tests until resolution. Consider dose reduction at investigator’s discretion.

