3.3 Removal of Subjects from Study

3.3.1 Criteria for stopping therapy:

- Substantial non-compliance with the requirements of the study.
- Any adverse event which, in the Investigator's opinion, requires termination of the study medication.
- Disease progression, unless at the discretion of the investigator (in collaboration with Bayer/Onyx) continued treatment with study drug is appropriate.
- The patient would benefit from additional radiation therapy beyond that specified in the protocol.
- Request by the patient or a legal representative/relative to stop the treatment.
- The patient presents with a beta-HCG test consistent with pregnancy. Pregnancy will be reported along the same timelines as a serious adverse event
- The patient uses illicit drugs or other substances that may, in the opinion of the Investigator, have a reasonable chance of contributing to toxicity or otherwise interfering with results.
- The development of a second malignancy that requires treatment, which would interfere with this study.
- The patient is lost to follow-up.
- Interruption in study drug's administration for greater than 3-week delay. Following surgery, interruption in study drug's administration is allowed for up to 10-weeks from initial surgery.
- Development of an intercurrent illness or situation which would, in the judgment of the investigator, affect assessments of clinical status and study endpoints to a significant degree.

3.3.2 Criteria for study withdrawal:

- Disease progression, unless at the discretion of the investigator (in collaboration with Bayer/Onyx) continued treatment with study drug is

appropriate.

- Study closure,
- Unacceptable adverse event(s),
- Patient decision to withdraw from the study, or
- In the judgment of the investigator, further treatment would not be in the best interest of the patient.

The Investigator will make every reasonable effort to keep each patient in the study unless it is in the patient's best interest to discontinue participation. If a patient is removed from the study or declines further participation, all End of Treatment evaluations should be performed if the patient is willing and able to be assessed. A description of the reason(s) for withdrawal from the study will be recorded on the case report form (CRF). The Investigator should also ensure that all patients are followed up for survival and recurrence after the Final Visit.

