5.1.1 Dose Modifications for Sorafenib for Hand-Foot Skin Reaction

Grade	Occurrence	Suggested Dose Modification
Grade 1 Minimal skin changes or dermatitis (e.g., erythema, edema, or hyperkeratosis) without pain	Any	Promptly institute supportive measures such as topical therapy for symptomatic relief and continue sorafenib treatment
Grade 2 Skin changes (e.g., peeling, blisters, bleeding, edema, or hyperkeratosis) with pain; limiting instrumental ADL	First	
Promptly institute supportive measures such as topical therapy for symptomatic relief and consider a decrease of sorafenib by one dose level for a minimum of 7 days and up to 28 days
 
 • If toxicity resolves to grade 0–1 after dose reduction, increase sorafenib back to previous dose level • If toxicity does not resolve to grade 0–1 despite dose reduction, interrupt sorafenib treatment for a minimum of 7 days and until toxicity has resolved to grade 0–1. 
 ▪ When resuming treatment after dose interruption, resume sorafenib at a one dose level reduction ▪ If toxicity is maintained at grade 0–1 at reduced dose for a minimum of 7 days and up to 28 days, increase back sorafenib to previous dose level
	Second or Third occurrence	
As for first occurrence. Upon resuming sorafenib, decrease dose by one dose level.
 
Decision whether to dose re-escalate should be based on clinical judgment and patient preference.

	Fourth occurrence	
Decision whether to discontinue sorafenib should be made based on clinical judgment and patient preference

Grade 3 Severe skin changes (e.g., peeling, blisters, bleeding, edema, or hyperkeratosis) with pain; limiting self care ADL	First occurrence	
Institute supportive measures such as topical therapy for symptomatic relief and interrupt sorafenib treatment for a minimum of 7 days and until toxicity has resolved to grade 0–1
 
 • When resuming treatment after dose interruption, decrease sorafenib by one dose level • If toxicity is maintained at grade 0–1 at reduced dose for a minimum of 7 days and up to 28 days, increase by one dose level
	Second occurrence	
As for first occurrence. Upon resuming sorafenib treatment, decrease dose by one dose level.
 
Decision whether to dose re-escalate should be made based on clinical judgment and patient preference.

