5.1.2 Dose Modifications for Sorafenib-Associated Hypertension

Hypertension is a known and potentially serious adverse event associated with sorafenib treatment. Patients will have their blood pressure monitored and recorded weekly during the first 6 weeks of therapy, either at the doctor's office or by using any calibrated electronic device (such as those found at a local drug store or pharmacy). Patients will record their weekly blood pressure during the first 6 weeks on their drug diary, a copy of which will remain in the research chart. If the patient's blood pressure is elevated at any time (>150/100), even outside clinic visits, they should contact their treating physician.

Grade (CTCAE v4.0)	Antihypertensive Therapy	Blood Pressure Monitoring	Sorafenib Dose
Grade 1	None	Routine	No change
Grade 2	Initiate monotherapy (suggest dihydropyridine calcium-channel blocker)	Increase frequency and monitor (by health professional) every 2 days until stabilized	No change
Grade 3	Add agent(s): Ca ⁺⁺ channel blocker (if not already used), K ⁺ channel opener (angiotensin blockers), beta-blocker, thiazide diuretic	Increase frequency and monitor (by health professional) every 2 days until stabilized; continue qod monitoring to stabilization after dosing restarted.	Hold* sorafenib until symptoms resolve and diastolic BP < 100 mm/Hg. Resume treatment at 1 dose level lower
Grade 4			Off protocol therapy

* Patients requiring a delay of > 21 days should go off protocol therapy

CTCAE v4.0 definitions

Grade 1: Prehypertension (systolic BP 120 - 139 mm Hg or diastolic BP 80 - 89 mm Hg)

Grade 2: Stage 1 hypertension (systolic BP 140 - 159 mm Hg or diastolic BP 90 - 99 mm Hg); medical intervention indicated; recurrent or persistent (≥24 hrs); symptomatic increase by >20 mm Hg (diastolic) or to >140/90 mm Hg if previously WNL; monotherapy indicated. Pediatric: recurrent or persistent (≥24 hrs) BP >ULN; monotherapy indicated

Grade 3: Stage 2 hypertension (systolic BP ≥160 mm Hg or diastolic BP ≥100 mm Hg); medical intervention indicated; more than one drug or more intensive therapy than previously used indicated. Pediatric: Same as adult

Grade 4: Life-threatening consequences (e.g., malignant hypertension, transient or permanent neurologic deficit, hypertensive crisis); urgent intervention indicated. Pediatric: Same as adult

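### After a first grade 3 infarction, arterial thromboembolism or hemorrhage attributable to sorafenib, the written default in 5.1.3 is to restart at the same dose

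*Combined protocol and SAP*

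**What the plan says.** Section 5.1 modifies sorafenib only for events at least partly attributable to it. Hand-foot reaction (5.1.1) and hypertension (5.1.2) have their own tables. Section 5.1.3 then gives a generic hematologic/non-hematologic table, a footnote and a list of exceptions.

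Myocardial ischemia/infarction and arterial thromboembolism appear nowhere in 5.1 as events with their own rule. Among the exceptions, bleeding appears only alongside low platelets, and that bullet leads back to the generic table: "Grade 3-4 thrombocytopenia with clinically significant bleeding: refer to table above".

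The generic non-hematologic row works as follows:

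- **First grade 3 event:** hold until grade 1 or less, "then resume treatment at the same dose level". A reduction comes only after a second grade 3 toxicity.
- **Grade 4 event:** hold until grade 1 or less, "then reduce one dose level and resume treatment, or discontinue at the discretion of the principal investigator".

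For grade 3 hypertension, 5.1.2 says "Resume treatment at 1 dose level lower", once symptoms have resolved and diastolic pressure is below 100. Grade 4 hypertension ends protocol therapy.

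Two general provisions apply throughout. Section 3.3.1 stops therapy for a study-drug interruption ("administration for greater than 3-week delay"), with an allowance of up to 10 weeks from initial surgery, and 4.7 has a matching 3-week limit for adverse events. Both sections also let the investigator stop treatment because of an adverse event.

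**The concern.** Section 6.1 lists myocardial ischemia/infarction among the drug-related events seen with sorafenib. It also names cerebral hemorrhage, transient ischemic attack and thromboembolism as medically significant events, while saying that causality for these has not been established. Patients on warfarin or heparin may enter under 3.1.7.

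For these events a clinician who follows the dosing table as written would return a recovered patient to full dose after a first grade 3 event. The nearest cardiac rule, 5.2.2.2, covers left ventricular dysfunction and heart failure, not ischemia or infarction. What is at stake is the safety of a rare patient. The primary endpoint and the sample size are not in question.

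**Working it through.** **1. The rules side by side**, for a patient at level 0 (400 mg/day) with a first event that recovers in time:

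| Event | Recovery needed | Restart after grade 3 | After grade 4 |
|---|---|---|---|
| Generic non-hematologic row (5.1.3) | grade 1 or less | 400 mg/day | 200 mg/day permitted, or stop |
| Hypertension (5.1.2) | symptoms gone, diastolic < 100 | 200 mg/day, no re-escalation stated | off protocol therapy |
| Hand-foot reaction (5.1.1) | grade 0-1 | 200 mg/day, then 400 mg/day possible | no grade 4 row |

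The hand-foot table is a weak comparator. Its column is headed "Suggested Dose Modification", and if the reaction stays at grade 0-1 on the reduced dose it allows return to full dose: "for a minimum of 7 days and up to 28 days, increase by one dose level". The useful contrast is hypertension, and it runs both ways. Diastolic 90-99 is still grade 2 by the definitions under 5.1.2, so hypertension may restart at a grade that the generic row would not accept. The generic row is stricter on recovery and looser on dose.

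**2. Against the entry exclusions**, taking the hold to begin at the event:

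- Infarction excludes for 6 months (3.2.2), and a thrombotic or embolic event, including stroke and transient ischemic attack, excludes for 6 months (3.2.5). On study, a restart must come within 3 weeks or, around surgery, within 10 weeks of the operation. Both limits are far shorter than 6 months.
- Non-pulmonary hemorrhage of grade 3 or higher excludes for 4 weeks before first dose (3.2.7). The ordinary limit of 21 days is shorter than 28 days. The postoperative allowance (70 days) can exceed it, so for bleeding the mismatch lies in the ordinary case.

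**3. Dose consequence, one example.** Sorafenib days in the section 4 table are 14 + 21 + 21 + 15 = 71 before surgery and 14 + 21 + 21 + 15 = 71 after, 142 in all. Suppose a grade 3 bleed on day 15, held for days 15-35 (21 days) and resumed on day 36. Days 36-71 leave 36 preoperative days:

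- same level: 36 × 400 = 14,400 mg
- one level lower: 36 × 200 = 7,200 mg

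**4. Frequency.** Section 6.1 puts ischemia/infarction in the band 0.1% to less than 1%, from monotherapy. With n = 20:

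- expected patients: 20 × 0.001 = 0.02 to 20 × 0.01 = 0.2
- P(at least one) = 1 − (1 − p)^20: 1 − 0.999^20 = 2.0% to 1 − 0.99^20 = 18.2%

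The band is not split by grade or by speed of recovery, so at these rates the group reaching the restart rule is no larger and probably smaller. The documents give no rate for hemorrhage or arterial thromboembolism, so none is computed.

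**5. Effect of a stricter rule on the primary endpoint.** Assume events are spread evenly over the 142 sorafenib days. The preoperative share is 71/142 = 0.5, so 0.01 to 0.1 of 20 patients would have an ischemic event before surgery. If every one of them turned from responder to non-responder, the expected response rate would fall by at most 0.1/20 = 0.5 percentage points.

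**6. Sample size.** The figure in 11.3 reproduces. With 20 patients and success at 9 or more responses, the exact one-sided error is 0.041 at 25% and power is 0.802 at 52%. Nothing here changes that.

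**The case against.** The strongest reply is that these events are already handled. A catch-all row covers them, 3.3.1 and 4.7 let the investigator stop for an adverse event, grade 4 carries an explicit option to discontinue, and the 3-week limit removes most patients left with a deficit above grade 1. Patients at highest risk are screened out (3.2.2, 3.2.5-3.2.7, 3.2.9), and INR is monitored on warfarin. Serious events go to the drug supplier within 24 hours, with monthly review by an oncologist of the monitoring committee. Only ischemia/infarction is listed as drug-related, and no document says that an arterial event must end sorafenib.

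Most of this stands, and it limits the weight of the point. It does not remove it. The same discretion exists for hypertension, yet there the authors still wrote a firm rule. Where the written default is full dose, discretion has to work against the table.

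Three stronger readings are tempting, and the documents do not support them:

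- **That the protocol has no rule, or compels a restart after an infarct.** It has a generic rule, and stopping is always open.
- **That the generic row is more permissive than the hypertension rule in every respect.** Its recovery threshold is the stricter of the two.
- **That the entry exclusions make the dosing row a contradiction.** They govern who enters, not dosing on study. They only show how cautious the authors were about starting sorafenib soon after such events.

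**Conclusion.** The point holds as an overly permissive written default for three kinds of event, when they are at least partly attributable to sorafenib and recover in time. From level 0 the default is 400 mg/day after a first grade 3 event, against 200 mg/day after grade 3 hypertension. After grade 4, 200 mg/day is permitted, against removal from protocol therapy for hypertension.

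The only frequency the documents support is the monotherapy band for ischemia/infarction: 0.02 to 0.2 expected patients in 20. A reader might infer that an event of this kind is likely in this trial. The documents do not support that: they give no rate for hemorrhage or arterial thromboembolism, and 6.1 describes those it lists as infrequent. The conclusion rests on the text, not on the frequency. It is a cheap safety improvement, worth making, with no bearing on the design.

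**What to change.** Add a row to 5.1.3 that takes precedence over the generic row, for events at least partly attributable to sorafenib:

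- (a) Arterial thromboembolism or myocardial ischemia/infarction, grade 3 or higher: discontinue sorafenib.
- (b) Hemorrhage, grade 4: discontinue sorafenib.
- (c) Hemorrhage, grade 3: hold to grade 1 or less, then resume at least one dose level lower, or discontinue.

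Add clarifying sentences. Hematuria attributed to ifosfamide stays under 5.2.2.3. Chemotherapy remains governed by all of 5.2, including the general hold and reduction in 5.2.2, so that an event attributed to both drugs does not get conflicting instructions. The limits in 3.3 and 4.7 are unchanged. Say also that grade 3-4 bleeding with grade 3-4 thrombocytopenia follows the new row.

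The cut-offs are clinical judgment, since the documents do not fix them. Grade 1-2 events, including a transient ischemic attack graded below 3, would stay on the generic row unless the sponsor sets a lower threshold.

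The cost is a short amendment, with no added patients, visits or tests. The downside is that the rare affected patient loses or reduces the remaining sorafenib, possibly before surgery. Resected specimens are still scored under 9.1, and on the ischemia/infarction band the expected response rate would fall by at most 0.5 percentage points.

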5.2 Chemotherapy Dose Modifications

Dose modifications for epirubicin and ifosfamide-related toxicity will be based on the following dose level schema. All patients will start treatment at dose level 0. Patients who require a reduction of dose below Dose Level –3 will be removed from the study.

Dose Level	Dose Epirubicin (mg/m ² D1-3)	Dose Ifosfamide (mg/m ² D1-3)
0	30	2500
-1	22.5	2500
-2	22.5	2000
-3	20	1750

5.2.1 Hematologic Toxicity

5.2.1.1 A treatment cycle may not begin unless the patient's absolute neutrophil count (ANC) is $\geq 1500/\mu\text{L}$ and platelet count is $\geq 75,000/\mu\text{L}$ (without transfusion).

5.2.1.2 **Grade 4 neutropenic fever, grade 3 neutropenic fever lasting >5 days, or grade 4 neutropenia for >7days:** reduce by one dose level for next and all subsequent cycles

5.2.1.3 **Grade 3-4 thrombocytopenia with clinically significant bleeding or grade 4 thrombocytopenia lasting >5 days:** reduce by one dose level for next and all subsequent cycles

5.2.1.4 **Anemia:** Institution of erythropoietin or darbopoietin at physician's discretion

5.2.2 Non-hematologic Toxicity

Patients who experience Grade 3 or 4 toxicity that is attributable to chemotherapy and not to the underlying disease should have chemotherapy held until the toxicity resolves to \leq Grade 1. Treatment should then be resumed at a

reduction of one dose level for the next and all subsequent cycles (see exceptions below). Patients who are delayed greater than 3 weeks due to non-resolution of such toxicity will be taken off study.

- 5.2.2.1 Nausea and Vomiting:** Grade 3 or 4 nausea or vomiting should be managed with anti-emetic adjustments (at treating physicians discretion) before a dose-reduction is performed
- 5.2.2.2 Cardiac Toxicity:** Patients who experience a Grade 3 or greater impairment in left ventricular function (decline of $\geq 20\%$ of baseline LVEF or symptomatic congestive heart failure) or Grade 3 or greater left ventricular systolic dysfunction should immediately be removed from protocol therapy.
- 5.2.2.3 Renal Toxicity:** Patients who experience grade 2 or greater Acute Kidney Injury or Hematuria should have therapy held until the toxicity resolves to \leq Grade 1. Treatment should then be resumed at the next lower dose level that includes a lower dose of ifosfamide (i.e. reduce from dose level 0 or -1 to dose level -2, reduce from dose level -2 to dose level -3) for the next and all subsequent cycles, at the discretion of the treating physician.
- 5.2.2.4 Electrolyte Wasting:** Electrolyte wasting, especially potassium and phosphorous, is a common effect of ifosfamide therapy due to renal tubular effects. Grade 3 or greater hypokalemia and/or hypophosphatemia should be managed with appropriate electrolyte replacement. If electrolyte wasting is refractory to replacement therapy, a dose reduction should be undertaken to the next lower dose level that includes a lower dose of ifosfamide
- 5.2.2.5 CNS Toxicity:** Patients who experience grade 3 or greater Encephalopathy should have therapy held until the toxicity resolves to \leq Grade 1. Treatment should then be resumed at the next lower dose level that includes a lower dose of ifosfamide (i.e. reduce from dose level 0 or -1 to dose level -2, reduce from dose level -2 to dose level -3) for the next and all subsequent cycles. If a patient is to be removed from study due to reaching the maximum allowable number of dose level reductions, and if these reductions were due to ifosfamide-related CNS toxicity, then the patient will be allowed to continue on treatment with omission of ifosfamide and continuation of epirubicin and sorafenib.

6. AGENT FORMULATION AND PROCUREMENT

6.1 Sorafenib (Nexavar)

Availability: Sorafenib will be supplied for this study

Product description: Sorafenib 200 mg is supplied as round, biconvex, red-film-coated tablets, debossed with the 'Bayer cross' on one side and '200' on the other side. The tablets contain sorafenib tosylate equivalent to 200 mg of the free base sorafenib, and the excipients croscarmellose sodium, microcrystalline cellulose, hypromellose, sodium lauryl sulfate, and magnesium stearate. The film-coat consists of

hypromellose, polyethylene glycol, titanium dioxide and red iron oxide. The film coating has no effect on the rate of release of the active sorafenib tosylate. Study Drug can be supplied as sorafenib 200 mg commercial tablets in bottles of 140 tablets with a product identification label affixed or as commercial Nexavar in bottles of 120 tablets.

Storage requirements: Do not store above 25°C (77°F). Store in the original package.

Stability: The current shelf life is 36 months.

Route of administration: Orally. Sorafenib should be given on an empty stomach 1 hour before 2 hours after a meal.

Pregnancy: Women should avoid becoming pregnant while on therapy. Women of childbearing potential must be apprised of the potential hazard to the fetus, which includes severe malformation (teratogenicity), failure to thrive and fetal death (embryotoxicity). Sorafenib should not be used during pregnancy. Breastfeeding should be discontinued during sorafenib therapy.

Expected adverse events: The following additional drug-related adverse events and laboratory abnormalities were reported from clinical trials of sorafenib in 1286 cancer patients who received sorafenib as monotherapy (*very common* 10% or greater, *common* 1 to less than 10%, *uncommon* 0.1% to less than 1%):

Cardiovascular: *Uncommon:* hypertensive crisis, myocardial ischemia and/or infarction

Dermatologic: *Very common:* erythema *Common:* exfoliative dermatitis, acne, flushing *Uncommon:* folliculitis, eczema, erythema multiforme

Digestive: *Very common:* increased lipase, increased amylase *Common:* mucositis, stomatitis (including dry mouth and glossodynia), dyspepsia, dysphagia *Uncommon:* pancreatitis, gastrointestinal reflux, gastritis. Note that elevations in lipase are very common; a diagnosis of pancreatitis should not be made solely on the basis of abnormal laboratory values

General Disorders: *Very common:* asthenia, pain (including mouth pain, bone pain, and muscle pain) *Common:* decreased appetite, influenza-like illness, pyrexia *Uncommon:* infection

Hematologic: *Very common:* leukopenia, lymphopenia *Common:* anemia, neutropenia, thrombocytopenia *Uncommon:* INR abnormal

Hypersensitivity: *Uncommon:* hypersensitivity reactions (including skin reactions and urticaria)

Metabolic and Nutritional: *Very common:* hypophosphatemia *Common:* transient increases in transaminases *Uncommon:* dehydration, hyponatremia, transient increases in alkaline phosphatase, increased bilirubin (including jaundice), hypothyroidism

Musculoskeletal: *Common:* arthralgia, myalgia

Nervous System and Psychiatric: *Common:* depression *Uncommon:* tinnitus

Reproductive: *Common:* erectile dysfunction *Uncommon:* gynecomastia

Respiratory: *Common:* hoarseness *Uncommon:* rhinorrhea

In addition, the following medically significant adverse events were reported

infrequently during clinical trials of sorafenib: cerebral hemorrhage, transient ischemic attack, cardiac failure, arrhythmia, thromboembolism, acute renal failure. For these events, the causal relationship to sorafenib has not been established.

Effects on fertility: Results from animal studies indicate that sorafenib can impair male and female fertility.

